#### *Recruitment of anesthesia staff*

Anesthesia staff (including residents and fellows) who are scheduled in the unit's OR will be informed of the study by staff anesthetists via their St. Michael's email addresses (see Appendix 1). All anesthesia staff will be invited to join an informative presentation about the study that will be held by one of the researchers at departmental Grand Rounds. After the presentation, the Research Coordinator will obtain written informed consent from all anesthesiology staff who wish to participate. If consent is declined or withdrawn by an anesthesia staff member, resident, or fellow, procedures will not be recorded when the

respective person is scheduled for the unit's OR list. Anesthesia staff, residents, and fellows will be informed that a decision not to participate in the study will not affect their rotation or professional standing at St. Michael's Hospital in any way. A reminder e-mail will also be sent to anesthesiology staff who are scheduled in the OR, but who did not provide informed consent or were unable to attend the Grand Rounds presentation

#### *Recruitment of surgical staff*

The project investigator as well as the participating staff surgeons in the Department of Gynecologic Surgery at St. Michael's Hospital will be study subjects in all observed procedures, and therefore will also sign the written informed consent. All gynecology surgical staff (including fellows and trainees) will be initially contacted about the study via e-mail and will be invited to attend an informative presentation at the next Grand Rounds session (see Appendix 1). Surgical residents will be contacted via e-mail by the Program Director's office. Occasionally, medical students participate in the unit's OR for clinical clerkships. The rotation plan of surgical clerkship students is known to the undergraduate medical education coordinator for Fitzgerald academy, St. Michael's Hospital, medical students scheduled for the unit's OR lists will be contacted through the medical student speaker as a student representative. Informed consent will be obtained from all surgical staff who wish to participate in the study. This will be obtained by the Research Coordinator at the end of the Grand Rounds presentation. Prior to the day of scheduled surgery, a reminder email will be sent to all staff who have not yet provided informed consent or who were unable to attend the Grand Rounds presentation.

#### *Declined or withdrawn consent*

The informed consent of all participants (patients, healthcare staff, residents and students) has the highest priority for the researchers. If any team member in the OR has not given consent or has previously withdrawn consent, the procedure will not be recorded. If a staff member agrees, he or she may be scheduled for a different OR. To ensure that all members of the operating team have given consent, the Research Coordinator will monitor the OR lists and staff schedules one day prior to the list to ensure valid informed consent is available of all team members scheduled for that day. For that purpose, the Research

Coordinator will keep a master log that contains all names and roles of participants that have given informed consent (Appendix 7). If an OR team member has not given valid consent or has withdrawn consent, the Research Coordinator will ensure that on that particular day no recording is made. Consent of staff members will be valid for 12 months. This is explained in the staff consent form. Every study participant can withdraw consent at any point in time during the study. If a participating staff member withdraws consent, no procedures will be recorded from that point on, if the respective staff member is present. A patient participating in the study can also withdraw consent at any point before her procedure. Both staff members and patients can withdraw consent for procedures that have already been recorded, if they do so within 48 hours of the procedure. In order to maintain the scientific integrity of the study and avoid bias, the recordings may not be withdrawn beyond the 48-hour timeframe, nor may the other data collected up to the point of withdrawal. Data from procedures that have already been video-audio recorded *and evaluated* while valid consent existed cannot be withdrawn. This is a requirement to maintain the scientific integrity of the study and this will be clarified in the consent forms.

The researchers acknowledge that the OR staff may feel pressured by the recording and the assessment of their performance. Nursing staff will only be evaluated with regards to non-technical and team skills. It is important to acknowledge, that individual performance of staff members will not be evaluated. Instead, the respective roles in the OR (primary surgeon, secondary surgeons, circulating nurse, scrub nurse) are evaluated, thus no names or subject numbers will be linked to the analysis of OR delays. Each procedure will only be linked to a patient code, to ensure procedure, team performance, and outcome can be correlated to this case. Healthcare staff will not appear on any data collection forms. Consent forms and the staff consent master log are the only documents containing healthcare staff names and will be kept secure in a locked office at all times that can only be accessed by the researchers. Consent forms of healthcare staff cannot be linked to a particular case.

To avoid any feeling of coercion or pressure to participate, the Research Coordinator who is not involved in surgical procedures can be contacted by the participants in order to withdraw informed consent. Contact details will be provided on the final version of the consent form. The Research Coordinator will keep the name of the person who has

withdrawn consent anonymous and delete their name from the master log to ensure no further procedures will be recorded when this staff member is in the OR. As an additional safety barrier, a sign will be affixed on all doors of the unit's OR to inform any person entering the OR that recording may be in progress (Appendix 9).

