#### **General Design**

##### *Study Subjects*

A minimum of sixty elective total laparoscopic hysterectomy procedures performed in one operating room of an academic tertiary care center during a twelve-month period will be included in this study. Procedures will only be excluded if data collection is in any part

incomplete or patient or OR staff consent was declined or withdrawn. Studying total laparoscopic hysterectomy was selected as a marker to analyze OR efficiency as this is a commonly performed procedure that requires moderate degree of complexity in equipment set-up and can be generalized to other laparoscopic procedures. Health professionals that will be participating in the study are OR nursing staff, technical (scrub) assistants, anesthesia staff, and surgeons. The nursing team involved in each procedure typically consists of one scrub technical assistant or nurse and one circulating nurse. The anesthesia team is typically represented by either a staff anesthesiologist or an anesthesia resident (who is always supervised by a staff anesthesiologist). The surgical team is comprised of the staff surgeon, and two other surgeons, typically a fellow and a surgical resident. The staff surgeon will be present during all cases and perform the majority of procedures however, some full procedures, or particular steps of procedures, will be performed by a clinical fellow or a surgical resident under staff surgeon's direct supervision, which is standard practice in teaching hospitals. Medical students will occasionally also be part of the surgical OR team as part of their surgical rotation during clinical clerkships.

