#### *Data collection*

All eligible procedures will be continuously video- and audio- recorded. A panoramic view of the entire OR will be obtained using multiple surveillance cameras. The inside view of the laparoscopic camera will be recorded, as it is already standard practice. Video and audio recordings will start once the patient has entered the operating room and the user has started capture. Recordings will end when the patient exits the room and the user ends capture. The video and audio recordings will be automatically encrypted at the point of capture and stored behind a secure firewall within St. Michael's hospital. The encrypted videos will be transferred by secure socket connection to a St. Michael's Hospital research center - the International Centre for Surgical Safety (ICSS) – which is also protected by a secure firewall, where the videos will remain in a 'badge-access-only' office, on a multiple-password-protected computer. Next, a single study staff member with access to this computer will decrypt the videos and "blur" any frames in which the patient's face and/or sensitive body parts (i.e. genital area, breasts) are visible in order to preserve the patient's anonymity and dignity. The study staff member will then re-encrypt the files which will remain encrypted in the same protected environment until a certified clinical data analyst (i.e. a non-study-staff employee of ICSS who is rigorously trained to review operative videos) decrypts the videos and analyzes the videos for variables of interest as described in detail below.

Patient demographics as well as diagnoses and risk factors will be collected on an electronic patient data sheet (Appendix 2). The information on the patient data sheet is important for the study to stratify the data for patient risk factors and to identify organizational factors such as delays and environmental influences such as time of day. Video- and audio- recordings as well as all other recordings of data will capture time but not date. The time of day is important, since some factors such as vigilance can be affected

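### Must the protocol admit an operator code because it keeps staff numbers out of the delay analysis?

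*Protocol*

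**What the plan says.** All references are to the protocol.

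**The bar.** Declined or withdrawn consent states that "no names or subject numbers will be linked to the analysis of OR delays". It adds that "Each procedure will only be linked to a patient code" and that "Consent forms of healthcare staff cannot be linked to a particular case". Ratings attach to positions, not people: "the respective roles in the OR (primary surgeon, secondary surgeons, circulating nurse, scrub nurse) are evaluated". Because a patient code is expressly allowed, the excluded subject numbers can only be those of staff.

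**No way back.** Under Data collection, the recordings "as well as all other recordings of data will capture time but not date". The video and audio files and the link to the patient's name are deleted at 30 days, after which the data are anonymous for good.

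**Who operates.** Recruitment of surgical staff refers to "The project investigator as well as the participating staff surgeons in the Department of Gynecologic Surgery", in the plural. Study Subjects says "The staff surgeon will be present during all cases and perform the majority of procedures", but also that "some full procedures, or particular steps of procedures, will be performed by a clinical fellow or a surgical resident". No headcount is given.

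**What is analysed.** Research Objectives (item 2) and Hypothesis & Novelty call for correlating skills and team performance with case duration, cancellations and efficiency. Statistical Analysis names descriptive statistics, a correlation concerning the team's awareness of incidents, and a logistic regression for non-technical and team factors. Primary Outcome Measure makes the incidence and categorization of delays primary. The skills associations are secondary.

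**The concern.** Skill ratings and operating speed both plausibly belong to a person. If a handful of people supply most of the 60 or more procedures, cases by the same operator are not independent, and an unadjusted correlation or logistic test will tend to reject too often. An association that arises between operators could reflect skills, but also experience or speed. Only a within-operator comparison could begin to separate these, and it needs to know which cases share an operator.

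A model term can normally be left to the analysis plan. Here the protocol rules out collecting the variable, so a later plan could not make the gap good. The results are also meant to inform a framework for improving individual and team performance, so the source of any association matters to the study's purpose.

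**Working it through.** The protocol states no significance level, effect size or power, so there is no figure of its own to reproduce. The check has two parts: how large the effect could be, and what a code would bring.

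**Inputs.** From the protocol: n = 60, the minimum in Study Subjects. Assumed: k operators, intra-operator correlation of the rating ρx and of duration ρy.

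**Design effect.** For an association with equal caseloads m = 60/k:

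DEFF = 1 + (m − 1) · ρx · ρy

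- k = 4, ρx = 0.3, ρy = 0.1: 1 + 14 × 0.03 = 1.42, effective n = 60/1.42 = 42
- k = 4, ρx = 0.5, ρy = 0.2: 1 + 14 × 0.10 = 2.40, effective n = 25
- k = 4, ρx = 0.2, ρy = 0.05: 1 + 14 × 0.01 = 1.14, effective n = 53
- k = 20, ρx = 0.5, ρy = 0.2: 1 + 2 × 0.10 = 1.20, effective n = 50

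**Simulated false-positive rate.** Unadjusted correlation test, nominal two-sided 5%, no true association. Columns give (ρx, ρy).

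| Operators (cases each) | (0.2, 0.05) | (0.3, 0.1) | (0.5, 0.1) | (0.5, 0.2) |
|---|---|---|---|---|
| 4 (15) | 6.1% | 8.6% | 11.3% | 17.2% |
| 6 (10) | 5.6% | 7.7% | 9.7% | 14.1% |
| 10 (6) | 5.6% | 6.1% | 7.5% | 10.5% |
| 20 (3) | 5.1% | 5.8% | 5.8% | 7.2% |
| 4 (36/8/8/8) | 6% | 8.0% | 9.5% | 14.7% |

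If ratings do not cluster by operator, the rate is about 5%. A harsher case (3 operators, ρx = 0.6, ρy = 0.3) gives 29%. For delay coded yes/no, with half the cases delayed, the logistic score test gives 7–14% with 4 operators and 6–7% with 20 over the last three columns.

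**What a code would bring.** An operator fixed effect brings the rate back to about 5% throughout. That answers the within-operator question. The overall association, which is what the protocol asks about, needs clustered variance with a small-sample correction. An ordinary large-sample sandwich with 4–10 operators rejects in 12–28%, worse than no adjustment. With the correction (CR2, Satterthwaite degrees of freedom) the level is 3–5% with 4 or more operators, but power at a true correlation of 0.35 falls:

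| Operators | Unadjusted | Clustered overall | Within operator |
|---|---|---|---|
| 4 | 68–74% | 28–38% | 59–67% |
| 6 | 70–76% | 38–51% | 56–64% |
| 10 | 75% | 50–60% | 53–60% |

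For scale, the correlation detectable with 80% power in 60 independent cases is tanh((1.96 + 0.842)/√57) = 0.355.

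For the overall association, the code therefore gives least where inflation is largest. Where it could work well, with many operators, there is little inflation to remove.

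**The case for a change.** The best argument for a change is that this cannot be mended later. Several people very probably fill the primary-surgeon role, the coordinator already checks OR lists and staff schedules against the consent log the day before surgery, and one random code per procedure is a single field. A role label does not show which cases share a person. The within-operator analysis would keep its level and a fair share of its power.

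The structural point stands: the text leaves no route to an operator identifier. Three parts of the argument do not carry.

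- **The premise is plausible, not established.** The protocol does not say whether the rated primary surgeon is the staff surgeon or whoever operates. If one person fills that role throughout, the surgeon ratings raise no issue.
- **Case mix is not out of reach.** Under Data collection, patient demographics, diagnoses and risk factors are recorded so that the data can be stratified. Measured case mix can be adjusted for without knowing the operator.
- **The code is not cheap.** The same person needs the same code over twelve months, so the key must outlive the 30-day deletion. Staff consent would have to be reworded, and one team member's refusal stops the recording, so weaker anonymity could cost cases. With few operators, colleagues could recognise one another by case volume. Where a fellow or resident does only some steps, one code misdescribes the case. Nursing and anesthesia, two of the three teams in the second objective, would remain unadjusted.

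Two lighter measures add little. A case number in surgical order addresses drift over time, not clustering by operator, and the protocol does not bar it now. Labelling the skills associations as exploratory and unadjusted for staff would only write down what the pilot design already implies.

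**Conclusion.** No change is needed. The protocol trades operator-level analysis for staff anonymity and gives its reason: staff may feel pressured by being recorded and assessed, so individuals are not evaluated. Nowhere does it promise operator-level inference, so nothing is contradicted.

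The cost falls on secondary associations in a pilot meant to build knowledge for later research. The point estimates of the primary outcome are unaffected. Under the assumed correlations (rating 0.2–0.5, duration 0.05–0.2) and 4 to 20 operators, the unadjusted correlation test rejects in about 5–17% of studies instead of 5%. More extreme assumptions give more, and a single operator or unclustered ratings give none. None of these inputs is in the protocol.

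Analysts can adjust for measured case mix and read the skills associations as hypothesis-generating, without correction for repeated staff. Whether to admit an operator code is a judgement about staff protection on which reasonable people would differ, not a correction of an error.

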#### *Data collection*

All eligible procedures will be continuously video- and audio- recorded. A panoramic view of the entire OR will be obtained using multiple surveillance cameras. The inside view of the laparoscopic camera will be recorded, as it is already standard practice. Video and audio recordings will start once the patient has entered the operating room and the user has started capture. Recordings will end when the patient exits the room and the user ends capture. The video and audio recordings will be automatically encrypted at the point of capture and stored behind a secure firewall within St. Michael's hospital. The encrypted videos will be transferred by secure socket connection to a St. Michael's Hospital research center - the International Centre for Surgical Safety (ICSS) – which is also protected by a secure firewall, where the videos will remain in a 'badge-access-only' office, on a multiple-password-protected computer. Next, a single study staff member with access to this computer will decrypt the videos and "blur" any frames in which the patient's face and/or sensitive body parts (i.e. genital area, breasts) are visible in order to preserve the patient's anonymity and dignity. The study staff member will then re-encrypt the files which will remain encrypted in the same protected environment until a certified clinical data analyst (i.e. a non-study-staff employee of ICSS who is rigorously trained to review operative videos) decrypts the videos and analyzes the videos for variables of interest as described in detail below.

Patient demographics as well as diagnoses and risk factors will be collected on an electronic patient data sheet (Appendix 2). The information on the patient data sheet is important for the study to stratify the data for patient risk factors and to identify organizational factors such as delays and environmental influences such as time of day. Video- and audio- recordings as well as all other recordings of data will capture time but not date. The time of day is important, since some factors such as vigilance can be affected

by circadian rhythms of individuals. Additionally, we will record if any cases were cancelled following the hysterectomy that was captured. All data records, documentation or information containing patient data will be de-identified with study numbers to ensure that persons outside of the study will not be able to identify the participating patients. The code will be kept on a password protected hard drive that will only be accessible by the Research Coordinator. The researchers will however be given access to the data sheets as required to enter additional information such as follow-up data.

The recorded, analyzed, de-identified video files will be retained until completion of the recording review period (30 days). After 30 days the video and audio files will be deleted. A small sample of “segments of interest” (i.e. short video segments deemed to be highly educational) may be kept beyond 30 days, however these will not contain any identifying information for either the patient or staff members. Any retained “segments of interest” will undergo further de-identification processes in which *all* faces are blurred and *all* voices are pitched, thus preserving the anonymity of all members of the operating room team throughout these segments. The research data will be stored and the code linking the case data to a patient name will be deleted at 30 days. After that, the data will be permanently anonymized.

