### **III. Research Objectives**

- 1) To prospectively identify patterns or chain of events leading to prolonged case duration in total laparoscopic hysterectomy procedure in a gynecologic surgical population.
- 2) To assess how non-technical skills and team performance of surgeon, nursing and anesthesiology teams correlate with case duration and subsequent cancellations.

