### *Primary Outcome Measure*

The primary objective of this study is to measure the incidence and categorization of intra-operative time delays. Secondary outcome measures will be the incidence of events leading to time delays when evaluating in retrospection, the interaction of non-technical skills and their impact on events leading to time delays, correlation of time delay to its root cause, the amount of time taken to complete a procedure, the number of canceled cases, and OR utilization (ratio of number of canceled/completed cases).

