#### *Statistical Analysis*

This observational study represents a pilot study. Therefore, an *a priori* analysis of statistical power and sample size cannot be performed (see also chapter *sample size*). Descriptive statistical analysis of defined events and outcomes will be performed. Correlation statistic will be performed to evaluate the team's conscious awareness of incidents and adverse events. Logistic regression analysis will be performed to identify influencing non-technical and team performance factors. A biostatistician will be involved in the statistical analysis of the results.

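### Cancellations are recorded per hysterectomy without the number of cases still scheduled, so the cancellation rate is diluted and the planned count and ratio cannot be derived

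*Protocol*

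**What the plan says.** Under Data collection the protocol states: "Additionally, we will record if any cases were cancelled following the hysterectomy that was captured". No other instruction for collecting cancellations appears in the text available. Three other parts of the protocol depend on this item:

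- Objective 2 (III. Research Objectives) asks how skills and team performance "correlate with case duration and subsequent cancellations".
- Primary Outcome Measure lists among the secondary outcomes "the number of canceled cases, and OR utilization (ratio of number of canceled/completed cases").
- Statistical Analysis says "Logistic regression analysis will be performed to identify influencing non-technical and team performance factors", without naming the dependent variable.

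Four statements decide what could be reconstructed later:

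- Study Subjects plans "A minimum of sixty elective total laparoscopic hysterectomy procedures performed in one operating room" over twelve months and sets no limit of one captured procedure per list.
- Data collection says "Video- and audio- recordings as well as all other recordings of data will capture time but not date".
- Declined or withdrawn consent says "Each procedure will only be linked to a patient code".
- Data collection adds that "the code linking the case data to a patient name will be deleted at 30 days", after which the data are anonymous for good.

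The patient data sheet (Appendix 2) and the list of time stamps and events (Appendix 3) are cited but not shown.

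**The concern.** A case can be cancelled after a hysterectomy only if one was scheduled after it. The item does not establish whether that was so. For a hysterectomy that is last on its list, the literal answer is no, whatever happened in the room. That entry cannot be told apart from a procedure that had cases waiting and lost none.

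Three things follow. The rate over all captured procedures is too low as an estimate of the risk when a later case exists. An entry of whether any case was cancelled gives neither a count of cancelled cases nor a count of completed ones. And if two captured hysterectomies precede the same cancelled case, both entries are positive for one event.

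An analysis plan cannot repair this. It can choose a model and an analysis set, but it cannot restore the number of cases at risk if nobody wrote it down and the link to the patient has been deleted.

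**Working it through.** **No figure to reproduce.** The protocol states no cancellation rate, list structure, effect size or power. The only number taken from it is the minimum of 60 procedures. All other values below are assumptions, shown as ranges.

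**1. Item against outcome.** The collection rule asks whether any case was cancelled; the outcome section wants a number and a ratio. Suppose 12 of 60 entries are positive. The number of cancelled cases could be 12, more than 12 (two cases lost behind one hysterectomy) or fewer than 12 (two hysterectomies before the same lost case). The completed cases on those lists are not recorded. This mismatch needs no assumption.

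**2. Dilution of the rate.** Let s be the share of hysterectomies with no later scheduled case and p the risk of a cancellation when there is one. Recorded rate = (1 − s) × p. Procedures at risk = 60 × (1 − s).

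| s | At risk, of 60 | Recorded rate, p = 0.10 | Recorded rate, p = 0.20 | Procedures with a cancellation, p = 0.10 / 0.20 |
|---|---|---|---|---|
| 0.20 | 48 | 0.080 | 0.160 | 4.8 / 9.6 |
| 0.33 | about 40 | 0.067 | 0.134 | 4.0 / 8.0 |
| 0.50 | 30 | 0.050 | 0.100 | 3.0 / 6.0 |

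**3. Association with team performance.** Compare two groups, weaker and stronger team performance, with assumed risks of 0.25 and 0.10 when a later case exists. True relative risk = 0.25/0.10 = 2.5; true odds ratio = (0.25/0.75)/(0.10/0.90) = 3.0.

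- *Same s in both groups.* The factor (1 − s) cancels, so the relative risk stays 2.5. At s = 0.20 the rates are 0.20 and 0.08, and the odds ratio is 0.2500/0.0870 = 2.875. At s = 0.50 they are 0.125 and 0.05, and it is 0.1429/0.0526 = 2.71. The risk difference falls from 0.15 to 0.12 and 0.075.
- *Weaker teams more often last (s = 0.50 against 0.20).* Rates are 0.125 and 0.08: relative risk 1.56, odds ratio 1.64.
- *Stronger teams more often last (s = 0.20 for weaker, 0.50 for stronger).* Rates are 0.20 and 0.05: relative risk 4.0, odds ratio 4.75.

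Relative measures are therefore nearly untouched unless list position differs between the groups compared. If it does, the error can go either way.

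**4. Double entry.** Let d be the share of lists with two captured hysterectomies that both precede the cancelled case. Assume every list has a later case and at most one cancellation, and p = 0.20 per list. Number of lists = 60/(1 + d); true cancellations = 0.20 × 60/(1 + d); positive entries = 0.20 × 60 = 12. Inflation = 1 + d.

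| d | Lists | True cancellations | Positive entries | Inflation |
|---|---|---|---|---|
| 0.10 | 54.5 | 10.9 | 12 | 1.10 |
| 0.25 | 48 | 9.6 | 12 | 1.25 |
| 0.50 | 40 | 8.0 | 12 | 1.50 |

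**The case against.** The strongest reply is that the sentence is narrative and does not define a field. The outcome section asks for a number and a ratio, so counts are evidently intended, and Appendix 2 or 3 may hold the fields. This stands as a condition on the fix. It does not remove the point, because the one rule that can be read does not deliver what the outcomes require.

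A reader might infer that Objective 2 is distorted, for example that longer cases placed last hide the effect of duration on cancellation. The protocol does not support that. Objective 2 treats duration and cancellation both as outcomes and has skills and team performance as predictors, so no duration-to-cancellation estimate is planned. Nothing in the text says that list position goes with skills, and without such a link the relative risk does not move.

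A reader might also infer that double counting will occur. The number of hysterectomies per list is not given, and the minimum of 60 in twelve months is little more than one a week. It is a possibility only. Tracing is not hopeless at first either: the Research Coordinator checks the OR lists the day before, the linking code exists for 30 days, and time of day is a rough proxy for position. After the code is deleted, however, nothing in the described data groups procedures by list.

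Finally, precision will be poor whatever is done: about 3 to 10 procedures with a cancellation under the assumptions above. That is true and limits what the change can buy for the association. It does not excuse a rate with the wrong denominator.

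**Conclusion.** The point holds as a defect of data collection for secondary outcomes. From the visible text, procedures with no later case would be read as having no cancellation, and the planned count and ratio cannot be obtained.

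The recorded rate is lowered by the factor 1 − s, that is by 20% to 50% for the assumed range of s. Bias in the skills association is conditional on list position being related to those predictors, and its direction is unknown. Double entry is possible, not shown, and would inflate counts by the factor 1 + d. All sizes rest on assumed s, p and d. That procedures with no later case are entered as no is the natural reading of the sentence, not a stated coding rule.

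The change is worth making before data collection because the loss cannot be reversed once the data are anonymous. The primary outcome, the incidence and categories of intra-operative delay, is not affected.

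**What to change.** First check Appendices 2 and 3. If the fields are not there, replace the sentence under Data collection with one to this effect: for each captured hysterectomy, the study will take from that day's OR list the number of cases scheduled after it, the number of those completed and the number cancelled, with the reason for each cancellation, and will assign a non-identifying list code shared by all captured procedures on that list.

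Then state two rules:

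- The association of skills and team performance with cancellation uses only procedures with at least one later scheduled case.
- In the totals, each cancelled case is counted once per list. Taking the counts from the earliest captured hysterectomy on a list achieves this, since whatever follows a later one also follows the first.

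Recording the reason is useful description. Restricting the outcome to cancellations for lack of time, or attributing each to one particular hysterectomy, would be a new choice that the protocol does not call for, and neither is needed here.

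The cost is a few fields copied on the day, with no date or name, and a smaller set for this secondary analysis (30 to 48 of 60 in the range above). The procedures left out had no case that could be cancelled. With about 60 procedures the association stays imprecise, and the report should say so.
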